**Variables:** The outcome in this study is myocarditis, categorized into three cohorts: 1) myocarditis post mRNA COVID-19 vaccination, 2) myocarditis post-SARS-CoV-2 infection, or 3) acute/viral myocarditis pre-2020. Myocarditis will be identified with ICD-10-CM codes in EHR and claims data. In addition, Brighton Collaboration Criteria will be used as the basis during manual reviews of electronic medical notes by two clinicians at Optum to validate a subset of the cases. Exposure variables will include potential risk factors for myocarditis including demographic characteristics, diagnoses and procedures defined with ICD-10 codes, treatments (prescriptions) and laboratory tests identified in the EHR. Covariates include medical comorbidities and other treatments at index, as well as healthcare utilization before index, and may include other factors not considered as risk factors for myocarditis.

**Data sources:** Optum's statistically de-identified Electronic Health Record (EHR) and Integrated Claims-Clinical dataset, which combines adjudicated claims data (where available) with Optum's EHR data, are the data sources for this study. In addition, this study will use data available in the medical records for a subset of myocarditis patients that have clinical patient notes and other data that cannot be mapped into the larger structured database.

**Study size:** Optum's longitudinal EHR repository is derived from dozens of healthcare provider organizations in the US, that include more than 57 contributing sources and 111K sites of care: treating more than 106 million patients receiving care in the US. Based on initial feasibility assessment of the Optum EHR database, there were approximately 240 myocarditis cases within 21 days of mRNA vaccination, 1,730 myocarditis cases after SARS-CoV-2 infection, and 7,200 myocarditis cases prior to 01 November 2019. In addition, the large size of the database will allow for matching of each myocarditis case with controls for the risk factor analyses.

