## 9.2. Setting

This study will use the US-based Optum's deidentified Electronic Health Record (EHR) data, with supplemental linkage to Optum's Integrated Claims-Clinical adjudicated claims dataset for those patients in the EHR who also have claims data available. For a subset of patients in the EHR, data exist including patient electronic clinical notes which will allow manual clinician review at Optum to confirm myocarditis cases based on available data that align with the Brighton Collaboration criteria. Review of clinical notes will not be conducted for the random sample of patients without evidence of myocarditis that will serve as controls for the risk factor analysis. Optum's role, processes, and data is described in more detail in Section 9.4.

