#### 9.3. Variables

As described above, patients in the myocarditis cohorts will be identified via ICD codes in the EHR data, and a subset will be confirmed using Brighton Collaboration criteria  and medical record review. The main study variables of interest, including demographics, diagnostic, therapeutic and laboratory/examinations are listed in **Table 1: Variables and associated roles.** Operational definitions, codes, more detailed listings of comorbidities, procedures and treatments, as well as any additional variables will be provided in the SAP.

Table 1. Variables and Associated Roles (Detailed Operationalization to be Described in SAP)

Variable	Role
Year of birth	Demographic
Sex	Demographic
Race/Ethnicity	Demographic
Geographic region (census regions)	Demographic
Payer type	Demographic
Date of matched encounter (index date for controls)	Index
Date of qualifying myocarditis diagnosis (index date for cases)	Diagnosis and index
Age at time of diagnosis (e.g., index date, or if unavailable then age entered or calculated in database closest to myocarditis diagnosis)	Diagnosis

Variable	Role
Time to diagnosis (time from first Optum EHR record until first myocarditis diagnosis date)	Diagnosis
Time since diagnosis (time from first myocarditis diagnosis date until last date in the Optum EHR or date of death)	Diagnosis
Laboratory biomarkers if feasible (e.g. troponin, CRP, CK-MB, CPK, additional lab markers TBD)	Diagnosis
Imaging* (e.g. echocardiogram, Cardiac MRI, Cardiac Magnetic Resonance, cMR, ECG)	Diagnosis
Procedures* (Biopsy / cardiac biopsy)	Diagnosis
mRNA COVID-19 vaccination	Exposure
SARS-CoV-2 infection	Exposure
Medical comorbidities prior to diagnosis/index date** (e.g. Charlson categories, Feudtner Complex chronic conditions [CCC] for pediatric populations, Healthcare Cost and Utilization Project Clinical Classifications Software [HCUP CCS] groups, incl. cardiac, immune, inflammatory conditions)	Medical history
Treatments prior to diagnosis/index date* (e.g. prior cardiac or COVID-related treatments, frequency of other drug classes)	Medical history
Procedures prior to diagnosis/index date* (e.g. cardiac, HCUP CCS groups)	Medical history
Labs of interest prior to diagnosis/index date* (e.g. labs mentioned above, as well as other cardiac labs, basic metabolic panel, complete blood count, urinalysis, thyroid test, lipid panel, cultures)	Medical history

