Prior HCU within the 6 months prior to diagnosis/index date (e.g. hospitalizations, emergency department, other outpatient visits)  * Populs of these tests will not be available, only whether the results support	Medical history

\* Results of these tests will not be available, only whether the results supported the Brighton Criteria.

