## 9.7. Data analysis

# **Primary objective**

In primary analyses, descriptive statistics will be presented to characterize myocarditis patients in terms of demographic and clinical characteristics (including clinical characteristics of the myocarditis episode, as well as clinical history of the patient) as of the index date (date of myocarditis diagnosis code for myocarditis cases, or matched month/year among the control group). Specific demographics and clinical characteristics of interest are described in Section 9.3. Descriptive statistics will include counts and percentages for categorical data. For continuous variables, we will provide statistics such as mean, median, standard deviation, and range.

Additionally, appropriate statistical models such as conditional logistic regression or generalized estimating equations (GEE) incorporating non-independence of observations will be described in greater detail in the SAP. These models will estimate odds ratios (ORs) and 95% CIs of associations between demographics, clinical characteristics, and empirical model identified risk factors (based on either a stepwise selection approaches or via statistical significance in univariate models) and myocarditis. Models may incorporate laboratory based prognostic indices, severity status, clinical risk factors noted in Section 9.3 along with potential empirical model identified risk factors. These models will be run for the myocarditis cases and controls identified with ICD-10-CM codes in the EHR, and according to the inclusion and exclusion criteria as provided in Section 9.2, as well as for the cases that are validated by clinician reviews as myocarditis using the available Brighton Collaboration Criteria and information in medical record notes, as specified in Section 9.6. Model parameters will be detailed in the SAP.

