#### 9.9. Limitations of the research methods

This study has several strengths. First, it is a population-based study in a real-world population, increasing generalizability and external validity. Second, the Optum EHR database has both inpatient and outpatient data, in addition to laboratory data and microbiology results for a subset of patients that could be leveraged. In addition, the large sample size will enable the capture of a range of pre-specified health outcomes and clinical conditions, while the longitudinal nature of the data will allow us the ability to track risk factors, clinical manifestations, and changes in prognostic laboratory values over time.

However, the study also has several limitations. As is the case in any study based on secondary data sources, outcome misclassification is a possibility, as delayed and misdiagnosis of myocarditis is potentially high. However, the validation sub-study, which is being conducted concurrently, will allow us to evaluate potential misclassification of myocarditis, as well as key risk factors of interest. Diagnostic codes may also be incorrect or may be included as part of the diagnostic rule-out process or a record of a historical myocarditis event rather than an indication of a recent myocarditis, however by incorporating a multi-tier treatment and diagnostic algorithm to identify myocarditis, it will allow us to evaluate the robustness and accuracy of cases identified based on diagnosed criteria alone versus criteria that requires additional data such as medication or procedures for verification of

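### Covariate windows include or run right up to the diagnosis-code date, and severity and laboratory indices may enter the case-control models, so work-up and early treatment of the episode can appear as risk factors

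*Protocol*

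**What the plan says.** **Timing of covariates.** The Abstract (Section 4, Variables) states: "Covariates include medical comorbidities and other treatments at index, as well as healthcare utilization before index". Section 9.7 describes demographic and clinical characteristics "as of the index date (date of myocarditis diagnosis code for myocarditis cases, or matched month/year among the control group"), so for a case index is the day the code was recorded. Section 8, by contrast, speaks of a baseline period before diagnosis. Table 1 in Section 9.3 places comorbidities, treatments, procedures and laboratory tests before the diagnosis or index date, and utilisation in the 6 months before it.

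**Content of the windows.** The prior-treatment row of Table 1 gives as examples "prior cardiac or COVID-related treatments, frequency of other drug classes". The prior-laboratory row refers back to the markers listed earlier in the table (troponin, CRP, CK-MB, CPK), which the table also gives the role Diagnosis. A footnote attached to the prior treatment, procedure and laboratory rows reads: "Results of these tests will not be available, only whether the results supported the Brighton Criteria".

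**The models.** Section 9.7 estimates odds ratios for demographics, clinical characteristics and factors chosen by stepwise selection or univariate significance. It continues: "Models may incorporate laboratory based prognostic indices, severity status, clinical risk factors noted in Section 9.3".

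**Controls.** Section 9.2 says: "Review of clinical notes will not be conducted for the random sample of patients without evidence of myocarditis".

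**The concern.** A risk factor must precede the disease. In a case-control analysis the covariate window therefore has to close before the disease process begins to generate records. Here the window either includes the code date (Abstract, Section 9.7) or runs right up to it (Table 1). The protocol's own limitations section says that "delayed and misdiagnosis of myocarditis is potentially high". If recognition is delayed, visits, troponin tests, imaging and first treatment can be on record before the code. In Cohorts 1 and 2 the open window also covers the time between the trigger and the code, up to 21 days after vaccination or 8 weeks after a positive test. Treatment of the infection can then count as history.

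Severity raises a related problem. Severity of the myocarditis episode has no counterpart in a control, so it cannot be a term in a model that contrasts cases with controls.

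What is at stake is the primary objective. Selection by significance favours strong associations, and records created by the episode can be among the strongest. The study could report consequences of myocarditis as its risk factors.

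**Working it through.** **Step 1: the passages side by side.**
- Abstract: comorbidities and other treatments at index; only utilisation before index.
- Section 8 and Table 1: before diagnosis or index.
- Section 9.7: characteristics as of the index date.

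These do not agree on whether the index day counts. None of them separates earlier history from the presenting episode, because no window closes before index. The protocol neither requires nor promises a lag.

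**Step 2: size of the bias.** The protocol has no figure to reproduce here; Section 9.5 states that sample size calculations do not apply. The following is an illustration under no true association.

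Inputs, all assumed: p0 is the share of controls with the record, and f is the share of cases that acquire it through the episode.

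p1 = p0 + f(1 − p0)

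OR = [p1/(1 − p1)] / [p0/(1 − p0)]

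For p0 = 1% and f = 10%: p1 = 0.01 + 0.10 × 0.99 = 0.109, and OR = (0.109/0.891)/(0.01/0.99) = 12.1.

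For p0 = 5% and f = 10%: p1 = 0.145, and OR = (0.145/0.855)/(0.05/0.95) = 3.22.

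For p0 = 20% and f = 10%: p1 = 0.28, and OR = (0.28/0.72)/(0.20/0.80) = 1.56.

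| Control prevalence p0 | OR, f = 5% | OR, f = 10% |
|---|---|---|
| 1% | 6.3 | 12.1 |
| 5% | 2.05 | 3.22 |
| 20% | 1.26 | 1.56 |

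**Step 3: chance of passing a univariate screen.** The case counts are the feasibility figures in Section 9.5: 240, 1,730 and 7,200. Further assumptions are a two-sided 0.05 screen, one control per case, and an unmatched comparison of two proportions.
- p0 = 5%, f = 10%: 94% with 240 cases, about 100% with 1,730 or 7,200.
- p0 = 20%, f = 5%: 18%, 81% and about 100%.

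Even a modest odds ratio of 1.26 would usually be selected in Cohort 2 and almost always in Cohort 3.

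**Step 4: after the change.** If the windows close before the episode starts, f = 0, so p1 = p0 and OR = 1. The selection rate returns to the nominal level of the screen.

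**The case against.** The strongest reply is that lags and covariate windows are ordinary SAP content. Sections 9.1, 9.3 and 9.7 defer index and episode definitions, operational definitions and model parameters to the SAP, and nothing forbids a lag. The at-index wording sits in the Abstract and describes covariates, which that paragraph lists apart from the candidate risk factors; Section 8 and Table 1 say before diagnosis. This stands in part: the SAP could still close the gap. But the protocol does state a timing and states it inconsistently. Moving the window end from index to just before it would not remove pre-code work-up. Calling a variable a covariate does not help either, since adjusting for something the episode produced can distort the other odds ratios.

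A reader might infer several stronger things that the documents do not support:

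- **That severity and laboratory indices will be in the models.** Section 9.7 only permits them, and it does not say that severity means severity of the myocarditis. The phrase "including clinical characteristics of the myocarditis episode, as well as clinical history of the patient" belongs to the descriptive statistics on myocarditis patients, not to the model sentence.
- **That the footnote makes these predictors case-only, with perfect separation from controls.** Section 9.6 runs the risk-factor models on structured data, and the Abstract takes treatments and laboratory tests from the EHR. The footnote restricts results, not whether a test or prescription occurred, and fits prescriptions poorly. It needs correcting but does not prove separation.
- **That the protocol says diagnosis is often delayed.** It says only that delay and misdiagnosis are potentially high, without a frequency.
- **That odds ratios of 6 to 12 or more are to be expected.** These need a control prevalence near 1%. Controls must have an encounter in the index month (Section 9.2.1), so they are people in care and higher prevalences are plausible.

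**Conclusion.** The concern holds as a risk that the protocol's wording permits, not as a bias certain to occur. The Abstract's timing conflicts with Section 8 and Table 1, no window stops short of index, and Section 9.7 allows laboratory prognostic indices and an undefined severity status into case-versus-control models with data-driven selection. Followed as written, this lets work-up and early treatment of the presenting episode appear as risk factors.

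Over the assumed range (control prevalence 1% to 20%, 5% to 10% of cases affected), a factor with no true effect would show an odds ratio between about 1.3 and 12. Both inputs are assumptions; the documents give neither. The screening probabilities also assume a 0.05 screen and 1:1 controls and ignore matching. The correction is inexpensive and worth making before the models are run.

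**What to change.** 1. **Timing.** In the Abstract, replace the at-index wording with a window that ends before the presenting episode, and bring Section 8, Table 1 and Section 9.7 into line.
2. **Same lag for both groups.** Apply the same lag relative to index to each case and its matched controls. The control criteria listed in Section 9.2.1 require neither a vaccination nor a positive test, so in Cohorts 1 and 2 the matched case's trigger-to-index interval can be carried over to its controls.
3. **Lag length.** The documents offer no basis for a particular value. Prespecify one and vary it in a sensitivity analysis. Factors arising between infection and diagnosis in Cohort 2 may be of interest in themselves and can be reported separately.
4. **Model terms.** In Section 9.7, limit episode severity and diagnostic or prognostic laboratory values of the episode to case-only description. Alternatively, state that severity status means baseline comorbidity severity that can be measured in controls.
5. **Footnote.** Correct the Table 1 footnote so that prior treatments, procedures and laboratory tests are structured-data records available for both groups.

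The cost is protocol and SAP wording plus a date shift in programming. The downside is that true conditions first recorded within the lag are not counted; the sensitivity analysis shows how much this matters.

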#### **Data analysis:**

#### Primary Objective:

In primary analyses, descriptive statistics will be presented to characterize myocarditis patients in terms of demographic and clinical characteristics (including clinical characteristics of the myocarditis episode, as well as clinical history of the patient) as of the index date (date of myocarditis diagnosis code for myocarditis cases, or matched month/year among the control group). Additionally, appropriate statistical models such as conditional logistic regression or generalized estimating equations (GEE) incorporating non-independence of observations will be described in greater detail in the SAP. Models will estimate odds ratios (ORs) and 95% CIs of associations between demographics, clinical characteristics, and empirical model identified risk factors (based on either a stepwise selection approaches or via statistical significance in univariate models) and myocarditis. These models will be run for the myocarditis cases and controls identified with ICD-10-CM codes in the administrative EHR and claims data, as well as for the cases that are validated by clinician reviews as myocarditis using available Brighton Collaboration Criteria and information in the medical record notes.

# **Secondary Objectives:**

In secondary analyses, all analyses above will be performed in the following *a priori* specified subgroups: 1) myocarditis case definitions in each cohort; 2) age group at index date, to be determined based on the distribution of cases (e.g. less than 40 years of age versus 40+ years; <18 years versus 18-39 years versus 40+ years); 3) sex; and 4) available follow-up time (years). In additional secondary analyses, we will assess the PPV of myocarditis diagnosis definitions that were created using algorithms in the EHR compared with those cases that are validated based on the review at Optum of the electronic medical notes.

# 5. AMENDMENTS AND UPDATES

Version Identifier	Date	Amendment Type (substantial or administrative)	Protocol Section(s) Changed	Summary of Amendment(s)	Reason
1.1	31	Administrative	Section 3.	Principal	Some Principal
	January		RESPONSIBLE	Investigator	Investigator/s no
	2024		PARTIES	Change	long with Pfizer
1.1	31	Administrative	Section 6	Update end of	Most recent data
	January		Milestones	data collection	available in the
	2024			and final study	database at time of
				report planned	data collection
				date	updated to 31
					March 2023
1.1	31	Administrative	Section 9.1. Study	Removal of	Requirements for
	January		Design	requirement for	notes now
	2024		Section 9.2.1.	minimum of 3	consistent for all
			Inclusion criteria	medical notes for	three Cohorts
				Cohorts 2 and 3	
1.1	31	Administrative	Section 9.6. Data	Addition of	Missing from
	January		management	sections	previous version of
	2024				the protocol to
					describe the data
					collection tools and
					record retention
					requirements
1.2	25 July	Administrative	Section 6	Update end of	Delays with the
	2024		Milestones	data collection	vendor for case
				and final study	adjudication and
				report planned	construction of the
	4.4		9 1 5	date	controls
2.0	11	Substantial	Section 6	Update end of	Updated study
	January		Milestones	data collection	milestone needs
	2025			and final study	and incorporated
				report planned	all former changes
				date	

#### 6. MILESTONES

Milestone	Planned date
Registration in the EU PAS register	25 May 2023
Start of data collection	26 May 2023
End of data collection	30 May 2025
Final study report	30 November 2025

#### 7. RATIONALE AND BACKGROUND

Myocarditis is an inflammatory disease of the myocardium diagnosed by established histological, immunological and immunohistochemical criteria. Clinically, myocarditis can present in a variety of ways, ranging from mild symptoms of chest pain and palpitations associated with transient Electrocardiogram (ECG) changes to life-threatening cardiogenic shock and ventricular arrhythmia . Myocarditis is a challenging diagnosis due to the heterogeneity of clinical presentations, and several classifications exist . During the COVID-19 era, diagnostic criteria have been based on those from the CDC and the Brighton Collaboration. The actual incidence of myocarditis is also difficult to determine as endomyocardial biopsy (EMB), the diagnostic gold standard, is used infrequently. It is estimated that approximatively 1.5 million individuals experience myocarditis per year worldwide, with the incidence varying from 1 to 40 per 100,000 depending upon the population characteristics. 

Although the aetiology of myocarditis often remains undetermined, a large variety of infectious agents, systemic diseases, drugs, and toxins can cause the disease. Molecular techniques suggest that viral infections are the most important cause of myocarditis in North America and Europe with genomes of enterovirus, adenovirus, influenza viruses, human herpes virus-6 (HHV-6), Epstein-Barr-virus, cytomegalovirus, hepatitis C virus, and parvovirus B19 reported in the myocardium of patients with myocarditis. In almost 50-80% of cases, no cause is ever found. 9

Outcome and prognosis of myocarditis depends on aetiology, clinical presentation, and disease stage. The fatality rate for myocarditis varies according to the methodology, geographic region, or time of the study, and generally converge to a rate of 5% myocarditis resulting in death in the short-term, and much higher if the acute episode required admission in intensive care or use of mechanical circulatory support, or if the myocarditis diagnosis was confirmed on histology. 10,11,12,13,14,15

To date, for myocarditis of any cause, only younger age, male gender, as well as engagement in competitive athletics were established as risk factors for myocarditis.  Population studies show that incidence of myocarditis tends to peak around adolescence through 40 years of age.  During pre-COVID-19 timeframes, the female-to-male ratio was between 1:1.5 and 1:1.7 in series of patients with myocarditis.  Outside of these characteristics, an understanding of risk factors that predispose individuals or contribute to the development of myocarditis after exposure to infections or drugs/vaccines is limited.

Higher myocarditis risk has been reported after SARS-CoV-2 infection, ranging from 5.4 per 100,000 persons (54 per million) for girls 5-11 years to 57.2 per 100,000 persons (572/million) for males 30 years of age or older within a 7-day risk window of infection. Heymans and Cooper

reviewed a variety of studies and concluded that SARS-CoV-2 infection caused 1000 to 4000 cases of myocarditis per 100,000 people, which was higher than most other reports. In a large meta-analysis, Ling et al. reported SARS-CoV-2 infection caused 1100 cases of myocarditis per 100,000 people. After the acute natural infection, from which most recover, long-term cardiovascular sequelae are possible. The risk and 1-year burden of cardiovascular disease in survivors of acute COVID-19 are substantial, with increased risk of cerebrovascular disorders (stroke, transient ischemic attack), dysrhythmias, ischemic and non-ischemic heart disease, pericarditis, myocarditis, heart failure, and thromboembolic disease.

Myocarditis has been reported as an AE following immunization with COVID-19 mRNA vaccine. In aggregate, epidemiology studies reported higher risk after Dose 2 compared to Dose 1 , shorter duration between Dose 1 and Dose 2 , and among younger males compared to older males or females of any age post-vaccination, with the highest excess risk reported in young males being <1 case per 10,000 vaccine doses. The clinical course of post-vaccination myocarditis and pericarditis tends to be mild, responds to standard of care treatments and requires a relatively short duration of hospitalisation (2-4 days). Short-term data on mortality is reassuring, with some studies showing a lower mortality compared with myocarditis of other causes, and other studies finding statistically comparable rates. The prognosis is comparable with myocarditis of other causes. Apart from male gender, younger age, and second dose, no other risk factors were identified for post-vaccine myocarditis.

Given limited information obtained to date, the objective of this study is to gain understanding of the risk factors for myocarditis in the US prior to and during the COVID-19 era. This study will examine the risk factors for myocarditis in general, as well as serve to advance the knowledge of myocarditis of various etiologies. Specifically, this study will examine and compare demographic and clinical characteristics that may be associated with risk of myocarditis after any dose of mRNA COVID-19 vaccine, myocarditis after SARS-CoV-2 infection (2020-later), or acute/viral myocarditis prior to COVID-19 (pre-2020). This study aims to provide a broader context for myocarditis following SARS-CoV-2 mRNA vaccination using a data source that has sufficiently detailed demographic and clinical information on a large number of patients, with medical chart review to adjudicate myocarditis cases via Brighton Collaboration criteria.  Identifying potential new risk factors for acute/viral myocarditis prior to the COVID-19 era, myocarditis after SARS-CoV-2 mRNA vaccine, or myocarditis after SARS-CoV-2 infection is important to contextualize and mitigate safety events while providing public health insights. In addition, this large-scale population-based study using real-world data (RWD) via EHR may help to identify risk factors that may differ from tertiary/referral center studies. A population-based view of patients' longitudinal journey that captures adequate medical history may also help inform potential future clinical trial inclusion/exclusion criteria, as well as generate hypotheses for potential myocarditis mechanisms of action.

This NI study is designated as a Post-Authorization Safety Study (PASS) and is conducted voluntarily by Pfizer.

